APPENDIX H: P-GP AND CYP3A INDUCERS/INHIBITORS

NOTE: Additional P-gp inducers/inhibitors or strong CYP3A inducers/inhibitors may become available while the clinical trial is ongoing. The following statements would apply to those medications in addition to those listed in the table below.

Patients who are receiving P-gp or strong CYP3A inhibitors concomitantly with LV should be closely monitored for adverse reactions. Based upon evaluation of the anti-CD30 MMAE ADC brentuximab vedotin (Adcetris) (ADCETRIS Prescribing Information, Seagen, June 2023), concomitant use of P-gp inhibitors or strong CYP3A4 inhibitors has the potential to increase the exposure to MMAE (the cytotoxic component of LV and brentuximab vedotin). Concomitant use of P-gp inducers or strong CYP3A4 inducers could decrease exposure to MMAE.

P-gp Inhibitors	Strong CYP3A Inhibitors
amiodarone	boceprevir
carvedilol	clarithromycin
clarithromycin	cobicistat
dronedarone	conivaptan
itraconazole	danoprevir and ritonavir
lapatinib	diltiazem
lopinavir and ritonavir	elvitegravir and ritonavir
propafenone	grapefruit juice
quinidine	idelalisib
ritonavir	indinavir and ritonavir
ranolazine	itraconazole
saquinavir and ritonavir	ketoconazole
telaprevir	lopinavir and ritonavir
tipranavir and ritonavir	nefazodone
verapami1	nelfinavir
	paritaprevir and ritonavir and (ombitasvir and/or dasabuvir)
	posaconazole
	ritonavir
	saquinavir and ritonavir
	telaprevir
	tipranavir and ritonavir
	troleandomycin
	voriconazole
P-gp Inducers/Strong CYP3A Inducers	
avasimibe	
carbamazepine	
phenytoin	
rifampin	
St John's wort	
tipranavir and ritonavir*	

^{*}P-gp inducer only.

APPENDIX I: NEW YORK HEART ASSOCIATION CLASSIFICATION

A Functional and Therapeutic Classification for Prescription of Physical Activity for Cardiac Patients

 $On-line\ source:\ http://www.heart.org/HEARTORG/Conditions/HeartFailure/AboutHeartFailure/Classes-of-HeartFailure_UCM_306328_Article.jsp$

APPENDIX J: RECIST CRITERIA SUMMARY (VERSION 1.1)

Response Evaluation Criteria in Solid Tumors

Term	Definition
Complete response (CR)	Disappearance of all target lesions. Any pathological lymph nodes must have reduction in short axis to <10 mm.
Partial response (PR)	$A \ge 30\%$ decrease in the sum of diameters of target lesions, taking as reference the baseline sum diameters.
Progressive disease (PD)	At least a 20% increase in the sum of diameters of target lesions, taking as reference the smallest sum on study (this includes the baseline sum if that is the smallest on study). In addition to the relative increase of 20%, the sum must also demonstrate an absolute increase of at least 0.5 cm. The appearance of one or more new lesions is also considered progression.
Stable disease (SD)	Neither sufficient shrinkage to qualify for PR nor sufficient increase to qualify for PD, taking as reference the smallest sum diameters while on study.
Measurable lesion	Must be accurately measured in at least one dimension (longest diameter in the plane of measurement is to be recorded) with a minimum size of 10 mm by CT scan (CT slice thickness no greater than 5 mm).

From RECIST Version 1.1 (Eisenhauer 2009)

A response (CR or PR) will be considered confirmed if the following disease assessment (at least 4 weeks after the initial response) still shows response (CR or PR). In cases where the initial response is followed by SD, it will be considered as confirmed if the SD is later followed by PR or CR. For example, if a patient had PR in week 8, SD in week 12, and PR in week 16, this PR will be considered as confirmed.

APPENDIX K: IRECIST: GUIDELINES FOR RESPONSE CRITERIA FOR USE IN TRIALS TESTING IMMUNOTHERAPEUTICS

Response will also be assessed using iRECIST guidelines (Seymour 2017). Immunotherapeutics may result in infiltration of immune cells leading to transient increase in the size in malignant lesions, or undetectable lesions becoming detectable. The criteria are identical to those of RECIST Version 1.1 in many respects but have been adapted to account for instances where an increase in tumor burden, or the appearance of new lesions, does not reflect true tumor progression.

Key differences are described below. All responses defined using iRECIST guidelines are designated with a prefix; iRECIST time-point and best responses will be recorded separately.

Confirming Disease Progression

Unlike RECIST Version 1.1, the iRECIST guidelines require the confirmation of progression and use the terms iUPD (unconfirmed progression) and iCPD (confirmed progression). Confirmatory scans should be performed at least 4 weeks, but no longer than 8 weeks after iUPD.

For iCPD to be confirmed, further increase in tumor burden, compared to the last assessment, must be seen as evidenced by 1 or more of the following:

- Continued increase in tumor burden (from iUPD) where RECIST Version 1.1 definitions
 of progression had been met (from nadir) in target, non-target disease or new lesions
 - Progression in target disease worsens with an increase of at least 5 mm in the absolute value of the sum
 - Continued unequivocal progression in non-target disease with an increase in tumor burden
 - Increase in size of previously identified new lesion(s) (an increase of at least 5 mm in the absolute value of the sum of those considered to be target new lesions) or additional new lesions.

Amendment 11: 19-Oct-2023

Page 117 of 152

RECIST Version 1.1 criteria are met in lesion types (target or non-target or new lesions)
where progression was not previously identified, including the appearance of additional
new lesions.

If iUPD is not confirmed at the next assessment, then the appropriate response will be assigned (iUPD if the criteria are still met, but no worsening, or iSD, iPR, or iCR if those criteria are met compared to baseline).

New Lesions

New lesions should be assessed and measured as they appear using RECIST Version 1.1 criteria (maximum of 5 lesions, no more than 2 per site, at least 10 mm in long axis (or 15 mm in short axis for nodal lesions), and recorded as New Lesions-Target (NLT) and New Lesion-Non-Target (NLNT) to allow clear differentiation from baseline target and non-target lesions.

New lesions may either meet the criteria of NLT or NLNT to drive iUPD (or iCPD). However, the measurements of target lesions should NOT be included in the sum of measures of original target lesions identified at baseline. Rather, these measurements will be collected separately in the source documents.

Amendment 11: 19-Oct-2023

Page 118 of 152

APPENDIX L: MYELOID GROWTH FACTOR SUPPORT RECOMMENDATIONS

For patients in Parts A and B: Primary Prophylaxis with granulocyte-colony stimulating factor (G-CSF) starting with the first cycle of LV and continuing through subsequent cycles is recommended for patients who have approximately 20% or higher risk of febrile neutropenia. Starting with Amendment 2 for patients in Parts A and B, G-CSF is required for patients weighing >80 kg at baseline, starting with their first cycle of therapy and at each subsequent cycle. Therefore, patients weighing >80 kg must not have contraindications to myeloid growth factors and must be willing to receive them.

For patients in Part C: Primary prophylactic G-CSF is not permitted in the DLT evaluation period during dose escalation.

For patients in Part D: Primary prophylactic G-CSF may not be appropriate because LV is given either weekly or on Days 1 and 8 every 21 days.

Patients in Parts A and B who experience Grade 4 neutropenia or febrile neutropenia of any grade in any cycle, must receive myeloid growth factors in all subsequent cycles. Myeloid growth factor support is also required for treatment of febrile neutropenia in Parts A and B.

Strongly consider primary prophylaxis when allowed per protocol based on patient, disease, and treatment risk factors, including the following:

Age ≥65 years

Advanced disease

Previous chemotherapy or radiation therapy

Pre-existing neutropenia or bone marrow involvement with tumor

Infection

Open wounds or recent surgery

Poor performance status or poor nutritional status

Poor renal function

Liver dysfunction, most notably elevated bilirubin

Cardiovascular disease

Multiple comorbid conditions

Secondary prophylaxis with G-CSF is recommended for patients in Parts C and D who experience a neutropenic complication with previous cycle of therapy (for which primary prophylaxis was not received), when dose reduction or delay may compromise treatment outcome with LV.

Treatment with G-CSF is strongly recommended for patients in Part C with fever and neutropenia who are at high risk for infection-associated complications or who have prognostic factors that are predictive of poor clinical outcomes. High-risk features include:

Sepsis syndrome (hypotension and multi-organ dysfunction)
Age >65 years
Profound neutropenia (absolute neutrophil count <0.1 x 10 ⁹ /L)
Uncontrolled primary disease
Pneumonia
Invasive fungal infection
Other clinically documented infections
Hospitalization at time of fever
Prior episode of febrile neutropenia

Refer to the Prescribing Information for the applicable G-CSF to determine the appropriate administration window for use with LV.

The choice of G-CSF is as determined by investigator.

Reference: (Crawford 2010; Smith 2015)

Amendment 11: 19-Oct-2023

Page 120 of 152

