3.1.2. Part B: Expansion

Part B is designed to further evaluate the safety and antitumor activity of the combination of LV and pembrolizumab and to maximize the benefit-risk profile. This part of the study will be conducted in 2 cohorts. Patients will enroll sequentially into Cohort 1 followed by Cohort 2. Part B Cohort 1 will receive the MAD of LV 2.5 mg/kg, (capped at 100 kg) in combination with pembrolizumab. Part B Cohort 2 will receive a dose of LV 2.0 mg/kg (capped at 100 kg), in combination with pembrolizumab (see Section 3.2.3.1 for rationale of Part B Cohort 2). Patients receiving >200 mg LV per infusion are required to be administered prophylactic granulocyte-colony stimulating factor (G-CSF).

Patients will receive LV and pembrolizumab q3wk. Pembrolizumab, 200 mg IV will be given per the US prescribing information on the same day as LV, approximately 60-90 minutes following LV infusion.

Approximately 73 patients will be enrolled in Part B of the study (approximately 48 in Cohort 1 and approximately 25 in Cohort 2).

The SMC and ISMC will continue to monitor the safety of LV and pembrolizumab. The SMC will meet regularly during Part A but convene as needed in Part B. The ISMC will meet periodically.

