5.2.3.2. Parts A and B

Prior to Amendment 2, LV at a dose of 2.5 mg/kg (capped at 80 kg per infusion) will be administered on Day 1 of every 21-day cycle by IV infusion given over approximately 30 minutes. For patients treated under Amendment 2 and later, the maximum weight cap per infusion will be increased from 80 kg to 100 kg. Any patient receiving >200 mg LV per infusion (weight >80 kg) is required to receive prophylactic G-CSF. For patients weighing ≥100 kg, dosing will be based on 100 kg. In consultation with the sponsor, eligible patients already on treatment prior to Amendment 2, may have their maximum weight cap per infusion increased to 100 kg or remain at 80 kg if they are receiving benefit (CR, PR, or SD).

Prior to Amendment 2, for patients weighing greater than 80 kg, dose calculations will be based on 80 kg (including dose reductions). For patients treated under Amendment 2 and later, the maximum weight cap per infusion will be increased from 80 kg to 100 kg, therefore, the maximum dose will be 250 mg per infusion when dosing at 2.5 mg/kg and 200 mg per infusion when dosing at 2.0 mg/kg. For patients who receive >200 mg LV per infusion, prophylactic G-CSF administration is required and will be given to patients on the day after study treatment is given, with a visit window of Day 2–4. Rounding is permissible within one milligram of nominal dose.

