5.5.1. Required Concomitant Therapy

Patients in Parts A and B: Starting with Amendment 2, it is mandatory that patients in Parts A and B who are administered >200 mg LV per infusion receive prophylactic G-CSF treatment starting with their first cycle of therapy at a >200 mg LV dose. It is also strongly recommended that these patients continue to receive prophylactic G-CSF at subsequent cycles regardless of the LV dose, if it is deemed to be needed per investigators' clinical judgement. Therefore, patients receiving >200 mg LV must not have contraindications to myeloid growth factors and must be willing to receive them. Additionally, patients in Parts A and B who experience Grade 4 neutropenia or febrile neutropenia of any grade in any cycle, must receive myeloid growth factors in all subsequent cycles. Myeloid growth factor support is also required for treatment of febrile neutropenia in Parts A and B. As per ASCO guidelines, prophylactic growth factors should start 1-3 days after LV administration. Myeloid growth factors (including pegfilgrastim) should not be given within 24 hours prior to the dose of LV. If pegfilgrastim is used, a one-time dose is recommended. If daily growth factor support is used, treat for at least 5-7 days or until the absolute neutrophil count is >1000/mm³ (< Grade 2).

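### Protocol Appendix L requires prophylactic G-CSF by baseline weight (>80 kg) and Section 5.5.1 by dose (>200 mg per infusion), so heavier patients at 2.0 mg/kg fall under one mandate and not the other

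*Protocol*

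**What the plan says.** **Appendix L (weight trigger).** For Parts A and B, the rule from Amendment 2 onwards reads: "G-CSF is required for patients weighing >80 kg at baseline, starting with their first cycle of therapy and at each subsequent cycle". Dose is not mentioned. Patients above 80 kg must therefore have no contraindication to myeloid growth factors and must be willing to receive them.

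**Section 5.5.1 (dose trigger).** From the same amendment, "it is mandatory that patients in Parts A and B who are administered >200 mg LV per infusion receive prophylactic G-CSF treatment", beginning with the first cycle given above 200 mg. For what follows, "It is also strongly recommended that these patients continue to receive prophylactic G-CSF at subsequent cycles regardless of the LV dose", subject to the investigator's judgement. The contraindication and willingness rule is attached to patients receiving more than 200 mg. The synopsis, Sections 3.1.1, 3.1.2 and 3.2.3 and the note to Table 3 also use the dose trigger.

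**Section 5.2.3.2 and Appendix A note M (both together).** Each states the requirement for doses above 200 mg and adds weight above 80 kg in brackets, as if the two were the same. Section 5.2.3.2 also gives the dose ceilings under the 100 kg cap: "the maximum dose will be 250 mg per infusion when dosing at 2.5 mg/kg and 200 mg per infusion when dosing at 2.0 mg/kg".

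**Where 2.0 mg/kg is used.** Section 3.1.2 says that "Part B Cohort 2 will receive a dose of LV 2.0 mg/kg (capped at 100 kg"). Section 9.1.2 plans about 25 patients in that cohort and about 30 at 2.0 mg/kg once Part A patients are added.

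**The concern.** A site treating a patient above 80 kg at 2.0 mg/kg finds a mandate in Appendix L and none in Section 5.5.1. Both are current text, and neither is said to take precedence.

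Two things are at stake. The first is conduct: whether primary prophylaxis is compulsory, and whether a heavier patient with a contraindication to growth factors may be treated at 2.0 mg/kg, depends on the page consulted. The eligibility criteria in Sections 4.1 and 4.2 do not address such contraindications. The second is interpretation: Section 3.2.3 reports that Grade 3 or higher neutropenia rose with dose in the monotherapy study, and Section 3.2.3.1 gives tolerability as a reason for Cohort 2. If sites followed different pages, neutropenia at 2.0 mg/kg would reflect a mixture of prophylaxis practices that the report should make visible.

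**Working it through.** **Inputs.** Dose levels, weight caps and dose ceilings from Sections 3.1.1, 3.1.2 and 5.2.3.2; re-dosing for a weight change of 10% or more from Section 5.2.3.1; the two triggers from Section 5.5.1 and Appendix L.

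**Formula.** Dose in mg = mg/kg × min(weight, cap).

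**Step 1: reproduce the protocol's ceilings.** 2.5 × 100 = 250 mg and 2.0 × 100 = 200 mg. Both match Section 5.2.3.2.

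**Step 2: weight needed to exceed 200 mg.** At 2.5 mg/kg, 200 / 2.5 = 80 kg, so more than 200 mg means more than 80 kg. At 2.0 mg/kg, 200 / 2.0 = 100 kg, which is the cap itself, so the dose can never exceed 200 mg.

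**Step 3: compare the rules under the 100 kg cap (weight unchanged from baseline).**

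| Weight | Dose at 2.5 mg/kg | 5.5.1 / App. L | Dose at 2.0 mg/kg | 5.5.1 / App. L |
|---|---|---|---|---|
| 80 kg | 200 mg | no / no | 160 mg | no / no |
| 81 kg | 202.5 mg | yes / yes | 162 mg | **no / yes** |
| 90 kg | 225 mg | yes / yes | 180 mg | **no / yes** |
| 100 kg | 250 mg | yes / yes | 200 mg | **no / yes** |
| 110 kg | 250 mg | yes / yes | 200 mg | **no / yes** |

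At 2.5 mg/kg the rules agree in every row. At 2.0 mg/kg they disagree for every patient above 80 kg.

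**Step 4: other cases where the rules part.**

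- *Dose reduction.* A 90 kg patient reduced from 2.5 to 2.0 mg/kg goes from 225 to 180 mg. Appendix L still requires G-CSF; Section 5.5.1 strongly recommends it, subject to judgement.
- *80 kg cap retained.* Patients already on treatment before Amendment 2 could stay on the 80 kg cap. Their ceiling is 2.5 × 80 = 200 mg, so only Appendix L requires G-CSF.
- *Weight gain.* A patient at 78 kg at baseline who gains 10% weighs 85.8 kg, and the dose becomes 2.5 × 85.8 = 214.5 mg. Section 5.5.1 requires G-CSF; Appendix L, which looks at baseline weight, does not.

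**Step 5: number affected.** Neither document states how many patients exceed 80 kg. At 2.0 mg/kg the range is 0 to about 30: about 25 in Cohort 2 and about 30 − 25 = 5 from Part A.

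**The case against.** **The instructions are not opposite.** A reader might infer that one page requires G-CSF and the other forbids it. The documents do not say that. Section 5.5.1 does not prohibit G-CSF at 200 mg or less. Section 5.5.2 strongly encourages growth factor support, including primary prophylaxis, with an exception for Cycle 1 in the dose escalation parts when the dose is not above 200 mg. In Cohort 2, giving G-CSF satisfies every passage. The nearest to a true clash is Cycle 1 of Part A at 2.0 mg/kg, if Part A counts as a dose escalation part. Even there Section 5.5.2 only withholds its encouragement, and the explicit Cycle 1 ban in Section 5.5.3 covers Part C alone. This objection stands and limits the point to required versus not required.

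**Later cycles at 2.5 mg/kg are mostly not in dispute.** A reader might infer that Section 5.5.1 makes every later cycle optional. But Section 5.2.3.2, the note to Table 3 and Appendix A note M require G-CSF for any infusion above 200 mg, with no first-cycle limit. The clear later-cycle conflict arises once the dose is no longer above 200 mg. This also stands.

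**The bracketed gloss in Section 5.2.3.2 is defensible.** It sits in a paragraph about 2.5 mg/kg, where it is exact under the 100 kg cap. It needs aligning, but it is not the source of the conflict.

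**No biased comparison follows.** A reader might infer that the inconsistency distorts a test of 2.0 against 2.5 mg/kg. No formal comparison is planned (Protocol 9.3.1.5, SAP 5.7), and the cohorts are sequential and descriptive. Even if every site followed Section 5.5.1, mandatory G-CSF would still differ between the two doses. The inconsistency therefore does not by itself create an imbalance, and choosing one trigger need not remove it.

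**Timing and existing tables.** Section 3.2.3.2 reports 88 patients treated in Parts A and B by 2 December 2019, against 85 to 97 planned (12–24 plus 73). Rewording in a 2023 version can change little first-cycle practice. The SAP already tabulates concomitant medications (6.7.3) and summarises by dose level unless otherwise specified (5.1). Both facts reduce the benefit of a change; neither removes the contradiction.

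**Conclusion.** The point holds as an inconsistency in an operative supportive-care rule. Appendix L and Section 5.5.1 use different triggers that agree only at 2.5 mg/kg under the 100 kg cap with weight near baseline. At 2.0 mg/kg the dose trigger cannot be met, while the weight trigger applies to everyone above 80 kg. The same split decides which patients must be free of contraindications to growth factors.

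The scope is primary prophylaxis. Sections 5.5.1 and Appendix L agree on mandatory growth factors after Grade 4 or febrile neutropenia and on their use to treat febrile neutropenia. The size at 2.0 mg/kg is between 0 and about 30 patients, because the weight distribution is not given. Patients in the three cases in Step 4 come on top and cannot be counted from the documents. The conclusion assumes that the 100 kg cap and the stated ceilings are applied as written; it does not depend on which trigger was intended.

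**What to change.** Reconcile Appendix L and Section 5.5.1 so that the protocol has one trigger for mandatory prophylaxis, one rule for later cycles (including after dose reduction or weight change) and one rule on contraindications. Then align the bracketed weight gloss in Section 5.2.3.2 and in Appendix A note M. Which rule applies is a clinical decision for the sponsor, and none is proposed here.

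Because the documents gave differing instructions to patients already treated, the study report should show G-CSF use by dose level beside the neutropenia and febrile neutropenia results, and state that the instructions differed. SAP 6.7.3 tabulates by drug substance name and does not call for growth factors to be grouped or set next to neutropenia, so one sentence in the SAP would be enough.

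The cost is wording in four places in the protocol and one additional display from concomitant medication data already collected. No new data are needed. The wording change will alter little past conduct; the display is what helps a reader of the results.

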APPENDIX M: MODIFIED TOXICITY PROBABILITY INTERVAL DESIGN SIMULATION REPORT

Introduction

Part C of this study evaluates weekly (q1wk) LV dosing (Day 1, Day 8, and Day 15 of every 3-week cycle). The primary objective of Part C is to evaluate the safety, tolerability, and identify the recommended dose of LV. Toxicity is measured by dose-limiting toxicities (DLTs) observed within the first cycle. Dose escalation in Part C will be conducted according to a modified toxicity probability interval method (mTPI).

DOSE ESCALATION

Overview

There will be 2 selected dose levels for LV in Part C. Intermediate doses of LV may also be evaluated during the execution phase at the discretion of the sponsor upon recommendation by the Safety Monitoring Committee (SMC).

The starting dose level of LV is 1.0 mg/kg. Dose escalation is conducted according to an mTPI method and according to a set of rules governing entry into the study and assignment of dose level. Decisions are described in Section 3.1.3 of the study protocol and detailed in this appendix. They are based on the posterior distribution of the DLT rate and derived independently for each dose level. The trial is closely monitored for safety and for identification of the MTD. If the SMC recommends exploration of an intermediate dose level, an additional dose level may be added.

Modified Toxicity Probability Interval Method

Dose escalation is conducted using the modified toxicity probability interval method. The implementation programs are available at: https://udesign.laiyaconsulting.com/.

For each dose level, i, the probability of a DLT on dose i is denoted by pi. The target toxicity probability in this study is defined as 25%, with a 5% margin. The equivalence interval is [20%, 30%], which contains the doses close to the true target DLT rate that physicians would deem acceptable for treating future patients. The equivalence interval partitions the unit interval (0, 1) into 3 subintervals: (0, 20%), [20%, 30%], and (30%, 1). Doses in these 3 intervals correspond to:

- Under dosing: pi <20%
- Proper dosing: 20% ≤ pi ≤30%
- Over dosing: pi >30%

In each dose level, the prior distribution of DLT probability, pi, is assumed to be non-informative Beta(1, 1). After each patient is treated and assessed for DLT, the posterior distribution of pi is updated to Beta(1 + xi, 1 + ni - xi), where xi and ni denote the number of DLTs and the number of DLT-evaluable patients at dose level i, respectively. The dose-escalation decision is based on the unit probability mass (UPM) on the posterior distribution of pi. For a given interval [a, b], the

UPM is defined as the ratio of the probability of the interval to the length of the interval, where for any DLT probability pi and

$$0 \le a < b \le 1$$

$$UPM(a, b) = Pr(a < pi < b) / (b - a)$$

After the toxicity outcomes are observed, the UPM on (0, 20%), [20%, 30%], and (30%, 1) at the current dose is calculated, and the dosing decision rules are:

- Escalate (E), if (0, 20%) has the largest UPM
- Stay at the current dose (S), if [20%, 30%] has the largest UPM
- De-escalate (D), if (30%, 1) has the largest UPM

In addition, the toxicity of a dose is defined as being unacceptable if there is more than a 95% probability that the DLT rate is higher than 25%,

Toxicity at dose i is unacceptable: Pr(pi >25%) >95%

If dose level i is determined to be unacceptable, the next patients are treated at dose level i-1 and doses i and higher are excluded from the trial. If i=1, the trial is terminated, and it is concluded that no dose level is safe, if there are no lower dose levels of interest to explore. The decision rules for each dose level are provided in Table 13.

Table 13: Decision rules for SGNLVA-002 – Part C, by mTPI for each dose level with target MTD = 25%

	Number of DLT-Evaluable Patients Treated at Current Dose									
		2	3	4	5	6	7	8	9	
	0	E	E	E	E	E	E	E	E	
8	1	S	S	S	S	E	E	E	E	
citi	2	Da	D	D	S	S	S	S	S	
Number of Toxicities	3		DU	DU	DU	D	S	S	S	
ofT	4			DU	DU	DU	DU	DU	D	
oer o	5				DU	DU	DU	DU	DU	
T T	6					DU	DU	DU	DU	
Z	7						DU	DU	DU	
	8							DU	DU	
	9								DU	

E=Escalate to the next higher dose, S=Stay at the current dose, D=De-escalate to the next lower dose, DU=Current dose is unacceptably toxic

At the end of the trial when the toxicity outcomes of all the enrolled DLT-evaluable patients are observed, a dose will be selected as the estimated MTD. The estimation is separated from the design for dose finding. The MTD is selected by performing an isotonic regression that borrows strength across doses. Let $\hat{p}i$ be the posterior mean of DLT rate. The pooled adjacent violators algorithm (PAVA) is applied on $\hat{p}i$ so that the resulting transformed values $\hat{p}i^*$ increase with the

a Dose will be de-escalated if the first 2 DLT-evaluable patients in a dose level experience DLT. Further evaluation of that dose level may be allowed if recommended by the SMC.

dose levels. That is, $\hat{p}i^* \le \hat{p}i+1^*$ for all i. The recommended MTD is the highest dose with a toxicity probability $\hat{p}i^*$ less than or equal to the target DLT rate 25%, i.e.,

Estimated MTD = max $\{i: \hat{p}i \le 25\%\}$

Dose-Escalation Rules

- 1. Dose escalation begins with patient enrollment to dose level of 1.0 mg/kg. At least 2 DLT-evaluable patients per dose level are required to escalate at any dose level. Once all patients in the previous cohort have completed DLT evaluation, patients can be enrolled to the next dose-level cohort. Subsequent enrollment and dose selection occurs via the following rules:
- If a dose level i is unacceptable, de-escalate to the lower dose level and never treat future
 patients at level i. If i = 1, stop the trial and conclude no dose is safe.

Interim Monitoring

The dose escalation will be closely monitored for safety and for identification of the MTD. If no doses are safe, dose escalation for that population will stop, and no MTD will be declared.

Safety Monitoring

If no doses are safe, dose escalation will stop, and no MTD will be declared. Formally, if

[figure not shown]
Pr(pi >25%) >95% for all i

Identification of the MTD

After each dose-level cohort, the estimation of MTD will be performed. If the model's next recommended dose is the same or below the MTD, the dose escalation may be stopped and MTD can be declared. Alternatively, if the model's next recommended dose is above the estimated MTD level, and patients have already been treated at the higher dose level, and the observed DLT rate at the recommended higher dose level exceeds the target DLT rate of 25%, the dose escalation may also be stopped and MTD can be declared.

Simulation Studies

To evaluate the operating characteristics of the dose-escalation design, simulation studies were performed for the following scenarios.

[figure not shown]

The plots illustrate the true DLT rate at each dose level. For Part C simulation, dose level 1 is 1.0 mg/kg and dose level 2 is 1.25 mg/kg. For example, Scenario 1 assume that MTD is 1.25 mg/kg, Scenario 2 assume that MTD is 1.0 mg/kg, and Scenario 3 assume that no selected dose is safe.

In each scenario, the dose-escalation and MTD-estimation process is replaced with 1000 replications. The probability of selecting an MTD, average number of DLT and the average number of patients treated, at each dose level is provided.

[figure not shown]
Amendment 11: 19-Oct-2023

Page 124 of 152

[figure not shown]
	Possible MTD Dose	Possible MTD Dose Level						
Scenario 1: MTD is 1.25 mg/kg	No dose is safe	1.0 mg/kg	1.25 mg/kg					
True DLT rate		0.12	0.22					
Mean number of patients at dose level		4.20	5.27					
				P (Select the True MTD) = 0.53				
Mean number of DLTs		0.52	1.19	Average DLT rate = 0.19				
at dose level				Average number of patients				
Pr (Chosen MTD)	0.10	0.37	0.53	above MTD = NA				

Pr=probability

Study SGNLVA-002 Clinical Protocol Ladiratuzumab Vedotin (LV; SGN-LIV1A) Seagen Inc. - Confidential

	Possible MTD Dose	Possible MTD Dose Level						
Scenario 1: MTD is 1.0 mg/kg	No dose is safe	1.0 mg/kg	1.25 mg/kg					
True DLT rate		0.22	0.40					
Mean number of patients at dose level		5.50	3.89					
Mean number of DLTs		1.23	1.57	P (Select the True MTD) = 0.49				
at dose level		1.23	1.57	Average DLT rate = 0.34 Average number of patients				
Pr (Chosen MTD)	0.35	0.49	0.16	above MTD = 3.9				

	Possible MTD Dose	Possible MTD Dose Level						
Scenario 1: MTD is 1.0 mg/kg	No dose is safe	1.0 mg/kg	1.25 mg/kg					
True DLT rate		0.35	0.4					
Mean number of patients at dose level		4.87	2.48	D.C. 1. 41 T. 3. 5770 314				
Mean number of DLTs at dose level		1.75	0.96	P (Select the True MTD) = NA Average DLT rate = 0.47 Average number of patients				
Pr (Chosen MTD)	0.62	0.25	0.13	above MTD = NA				

